4.4.2 Male Contraception

Male participants must agree to take all necessary measures to avoid causing pregnancy in their sexual partners during the study and for 30 days after the last dose of IP. Medically acceptable contraceptives include surgical sterilization (such as a vasectomy) and a condom used with a spermicidal gel or foam.

Male participants should not donate sperm during the study and for 30 days after the last dose of IP.

4.5 Discontinuation of Participants

A participant may withdraw, or their parent, guardian, or LAR may withdraw the participant from the IP administration and/or the study at any time for any reason without prejudice to their future medical care by the physician or the institution. The investigator or Sponsor may withdraw the participant at any time (e.g., in the interest of participant safety). The investigator is encouraged to discuss withdrawal of a participant from IP with the Medical Monitor, when possible, unless due to progression to an IV anesthetic for seizure suppression.

4.5.1 Investigational product discontinuation

Participants who discontinue IP without a taper (e.g., were administered IP for less than 2 hours, progress to anesthesia for seizure suppression or discontinue IP due to safety or any other reason, except due to withdrawal of consent) will have the follow-up assessments/procedures collected

every 24 hours through 120 hours (or until hospital discharge) and at the time of hospital discharge, followed by weekly follow-up visits/contacts at Week 1, 2, 3 and 4.

4.5.1.1 Reasons for IP discontinuation include, but are not limited to, the following:

- Adverse event or imminent safety concern
- Medical procedure
- Lack of efficacy with progression to high dose IV anesthesia for seizure/SE control
- Lack of efficacy without progression to high dose IV anesthesia for seizure/SE control
- Progression to high dose IV anesthesia for reason not related to seizure/SE
- Death
- Consent withdrawal
- Physician decision (must be specified in the participant's source documents and electronic case report form [eCRF])
- Other (must be specified in the participant's source documents and eCRF).

4.5.1.2 Study Withdrawal

All participants reserve the right to withdraw from the clinical study at any time, as stated in the informed consent/assent form.

Participants who terminate early from the study (e.g., due to consent withdrawn), any outstanding procedures and the evaluations listed for the Early Termination Visit in [Table 1](#) should be completed when early termination is being considered.

4.5.2 Participant Withdrawal Criteria

The Sponsor is not providing formal thresholds to discontinue a participant from the study. The Sponsor encourages the investigator to continuously assess any potential risks and benefits of participation during the entire study. The investigator should not hesitate to discontinue a participant from the clinical study if, according to the investigator's clinical judgment, the risks exceed any potential benefits. Reference examples below.

1. If the participant experiences worsening and persistent ventilatory depression despite routine clinical interventions (e.g., jaw thrust, chin lift or oxygen supplementation) that, in the judgment of the investigator, can be improved upon by discontinuation of the IP, the investigator may choose to discontinue such participant from the study. If positive ventilatory support is initiated and the participant is stable as per the investigator's clinical judgment, IP may be continued.
2. ECG evidence of QT prolongation (QTcF >500 msec, or an increase of QTcF >60 msec above baseline to a value >480 msec on the 12 lead ECG, confirmed on a repeat 12-lead ECG taken after resting at least 5 minutes in a supine or semi recumbent position after the original finding of prolonged QTcF).
3. Kidney function impairment such that eGFR ≤ 44 mL/min/1.73m² and participant is not starting dialysis.

4. Any other adverse event or safety issue (e.g., severe persistent hypotension/hypertension or tachycardia/bradycardia) that suggests it is not in the participant's best interest to continue to receive IP.
5. Rash that is clinically significant and considered to be related to the IP (e.g., morbilliform, urticarial, papular).
6. Participant experiences an SAE considered to be related to the IP.

Decisions to discontinue from the study will be made by the investigator. If feasible, the reason for discontinuation should be discussed with the Medical Monitor prior to the participant's discontinuation unless due to the progression to anesthesia for seizure suppression.

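### Protocol 4.5.2 gives reasons for stopping IP as examples for leaving the study, so a literal reading can end scheduled safety follow-up that other sections require

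*Protocol*

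**What the plan says.** **Follow-up rule.** Protocol 4.5.1 and 7.1.3 apply the full follow-up schedule to participants who "discontinue IP due to safety or any other reason, except due to withdrawal of consent". The Synopsis (infusion precautions; dose adjustments; study follow-up and discontinuation) and Section 6.2.7 say the same in general terms: stopping IP does not end participation, and only withdrawal of consent ends follow-up early. Section 5.2.2 keeps participants who progress to an IV anesthetic in the study.

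**Section 4.5.2.** It sets no formal thresholds, but says: "The investigator should not hesitate to discontinue a participant from the clinical study if" risks outweigh benefits in the investigator's judgment. Six examples follow:

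1. Ventilatory depression that "can be improved upon by discontinuation of the IP, the investigator may choose to discontinue such participant from the study".
2. QTcF prolongation.
3. "Kidney function impairment such that eGFR" is at or below 44 mL/min/1.73m² in a participant not starting dialysis.
4. Any other event that makes continued IP unwise.
5. Clinically significant rash related to IP.
6. "Participant experiences an SAE considered to be related to the IP".

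The closing sentence of 4.5.2 asks for discussion with the Medical Monitor before "discontinuation unless due to the progression to anesthesia for seizure suppression".

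**Consequence of leaving the study.** The Synopsis (study follow-up and discontinuation) exempts participants terminated early from the follow-up assessments and the Week 1 to 4 contacts. Section 4.5.1.2 gives them one Early Termination set, done when leaving is being considered.

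**The concern.** Two instructions cover the same participant and point in opposite directions. Someone whose eGFR falls or QTcF lengthens during infusion needs IP stopped. Under 4.5.1 that person stays in scheduled follow-up. Under 4.5.2 the investigator is encouraged to consider taking the person out of the study, which ends the schedule.

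These are the participants whose course after exposure is most informative about safety. Section 6.2.4 promises renal monitoring throughout the study because of Captisol, with urinary biomarkers reviewed by the DMC. An eGFR at or below 44 is nevertheless a listed example for leaving that monitoring. Later descriptive outcomes (SRSE, anesthesia through 4 weeks, mRS, EQ-5D-5L) would also be cut short.

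**Working it through.** **Text comparison.** The protocol gives no rate or threshold for these withdrawals, so the first step is to ask whether the 4.5.2 examples concern IP or the study.

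- Item 1: the remedy is stopping IP, and the stated alternative after ventilatory support is that IP may continue. The action named is nonetheless study discontinuation.
- Item 3: 44 is the upper bound of stage 3B in exclusion criterion 9 (Section 4.2), a limit on who may be exposed. It gives no reason to stop observing.
- Item 4: it turns on whether the participant should go on receiving IP.
- Closing sentence: it treats progression to anesthesia as a case of study discontinuation, but 5.2.2 keeps those participants in. The parallel sentence in 4.5 has the investigator "encouraged to discuss withdrawal of a participant from IP with the Medical Monitor, when possible, unless due to progression to an IV anesthetic", which concerns IP.

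The examples fit IP discontinuation; the action attached to them is study discontinuation.

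**Scheduled timepoints at risk.** Inputs are Table 1 footnotes g, i and j and Table 7. Table 7 counts 5 required biochemistry collections. Footnote i reproduces this as predose, IP discontinuation, 24 h after, hospital discharge and one weekly visit: 1 + 1 + 1 + 1 + 1 = 5. Footnote j states one weekly visit for urine chemistry directly.

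For withdrawal at IP stop, remaining = total − already done, and net loss = remaining − 1 Early Termination set.

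| Set | Scheduled | Done by IP stop | Remaining | Net loss |
|---|---|---|---|---|
| Chemistry (eGFR if available) | 5 | 2 (predose, IP discontinuation) | 5 − 2 = 3 | 3 − 1 = 2 |
| Urine NAG, β2-microglobulin, creatinine | 4 (predose, 24 h after, discharge, one weekly) | 1 (predose) | 4 − 1 = 3 | 3 − 1 = 2 |
| Safety ECG | 5 (predose, 2 h, IP discontinuation, 24 h after, discharge) | 3 | 5 − 3 = 2 | 2 − 1 = 1 |

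The ECG row assumes the infusion ran at least 2 hours.

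**When the loss is smaller.**

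- Trigger after the 24 h collections: chemistry and urine each have 3 − 1 = 2 remaining (net 1), and ECG has 2 − 1 = 1 remaining (net 0).
- Discharged participant with no in-person weekly visit: chemistry and urine again have 2 remaining (net 1), and ECG is unchanged.

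**Visits.** Visits 5–9 (24 to 120 h) are 5, Visit 10 (discharge) is 1 and Visits 11–14 (Weeks 1–4) are 4. That is 5 + 1 + 4 = 10, against one Early Termination visit. Ten is a ceiling: the 24-hourly visits stop at discharge, and the discharge visit can stand in for a weekly one (Section 7.1.3).

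**What remains after study exit.** Section 8.1 requires adverse events to be followed, with closure defined as an outcome, stabilization or an explanation. Section 7.1.3 follows unresolved events to closure, but in the context of the follow-up contacts that early termination removes. Section 7.2.3.7 allows unexplained abnormal values to be repeated, at the investigator's or Sponsor's discretion. Sections 8.2.2 and 8.2.4 keep SAE reporting, including related SAEs discovered later. None of these schedules a creatinine, urine biomarker or ECG.

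**The case against.** The strongest reply is that 4.5.2 uses the word study loosely where it means IP. It is permissive throughout, two of its examples speak of IP, and several other sections say plainly that participants who stop IP for safety continue. A site reading the whole protocol would probably keep following them. This stands to the extent that loss of follow-up is possible rather than required, and the documents show no instance of it. It does not remove the conflict, because "The investigator should not hesitate to discontinue a participant from the clinical study if" is active encouragement and the Synopsis exemption gives it effect.

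Three stronger readings are tempting, and the documents do not support them.

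- **That a participant withdrawn for eGFR or QT has no further follow-up of the abnormality.** Section 8.1.5 does limit its investigate-until-resolved rule to study completers. But it also makes a clinically significant change an adverse event, and the provisions in 7.1.3, 7.2.3.7 and 8.1 then bear on it. The 8.1.5 limit also excludes anesthetized participants, so 4.5.2 did not create it.
- **That the primary result is threatened.** SAP 3.2.1.1 scores discontinuation of study treatment as non-response, so the co-primaries are largely protected. SAP 3.2.2.1 censors time to SE cessation at discontinuation without saying whether of IP or study. That ambiguity is a separate matter and exists whatever 4.5.2 says.
- **That the general power in Section 4.5 to withdraw a participant for safety should be removed.** An investigator may have good reason to end study procedures as well as IP. Table 7 puts adult blood draws at 140.3 to 190.4 mL. Correcting 4.5.2 does not require touching that power.

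**Conclusion.** The concern holds as a contradiction between operative rules, with a modest, safety-side consequence. A site following 4.5.2 to the letter can end scheduled collection in a participant who only needed IP stopped.

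The net loss per such participant is at most 2 chemistry, 2 urine-biomarker and 1 ECG timepoints. This assumes withdrawal at IP stop after at least 2 hours of infusion, one weekly sample, and an Early Termination set that is actually obtained. Because that set is taken near exit, it says little about the later course. Later outcome assessments are lost too, but SAP 3.2.3 analyzes them descriptively only.

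The documents do not say how many participants were, or could be, withdrawn this way, so no trial-level effect can be stated. Section 3.1.1 reports that randomization stopped at 100, and participation lasts about 4 weeks. Any benefit of a change is confined to participants still in follow-up, and the documents do not show whether there are any.

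**What to change.** 1. Retitle the 4.5.2 list as examples of reasons to discontinue IP.
2. In item 1 and in the closing sentence, refer to discontinuation of IP, matching the parallel sentence in 4.5.
3. State in 4.5.2 that participants stopped for these reasons remain in the study for scheduled safety and outcome collection through Week 4, unless consent is withdrawn, they die or they are lost to follow-up.
4. Add a note to 4.5.3 that an adverse event leading only to IP discontinuation is recorded under 4.5.1.1 and is not by itself a reason for study discontinuation.
5. Leave the investigator's and Sponsor's general withdrawal power in 4.5 as it is.

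The cost is a site clarification letter or a short protocol edit. It adds no visits or samples beyond the existing schedule and leaves investigators free to stop IP. It needs no SAP change, because SAP 3.1.1 already summarizes reasons for stopping treatment and for leaving the study.

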4.5.3 Reasons for Study Discontinuation

The reason for study discontinuation must be determined by the investigator and recorded in the participant's medical record and in the eCRF. If a participant is withdrawn for more than one reason, each reason should be documented in the source document and the most clinically relevant reason should be entered in the eCRF.

Reasons for discontinuation include, but are not limited to, the following:

- Adverse event
- Protocol deviation
- Consent withdrawal
- Lost to follow-up
- Lack of efficacy
- Death
- Physician decision (must be specified in the participant's source documents and eCRF)
- Other (must be specified in the participant's source documents and eCRF)

4.5.4 Participants Lost to Follow-up Prior to Last Scheduled Visit

A minimum of three documented attempts must be made to contact any participant lost to follow-up at any timepoint prior to the last scheduled contact (office visit or telephone contact). At least one of these documented attempts must include a written communication sent to the participant's last known address via courier or mail (with an acknowledgment of receipt request) asking that they return to the site for final safety evaluations. If a contact is not made, the participant should be classified as Lost to Follow-up in the eCRF. However, if contact is made but the participant refuses or is unable to come to the final safety evaluation, they should be classified as Other and the reason documented in the eCRF.

5 PRIOR AND CONCOMITANT TREATMENT

5.1 Prior Treatment

Prior treatment includes all non-study treatment (including AEDs) administered within 14 days of IP initiation (or pharmacokinetic equivalent of five half-lives, whichever is longer).

Treatments including but not limited to herbal treatments, vitamins, surgical implants (such as Vagus nerve stimulator), and prescribed medications, if available, must be recorded on the appropriate eCRF page.

Benzodiazepines, AEDs and Anesthesia Medications

- Prior to IP initiation (not experiencing a seizure event)
 - Medications administered during this timeframe will be collected per the medication order
- Prior to IP initiation (for the current SE event)
 - Medications administered during this timeframe will be collected separately (i.e., each dose administered will be collected separately)

Vasopressors

- The administration of a continuous IV vasopressor infusion in the 24-hours prior to IP initiation will be collected in the Prior and Concomitant Medication eCRF

5.2 Concomitant Treatment

Concomitant treatment refers to all treatment taken between the date of the first dose of IP and the final study follow-up visit/contact.

Concomitant treatment information must be recorded on the appropriate eCRF page.

Benzodiazepines, AEDs and Anesthesia Medications

- During IP administration and for 120 hours of the follow-up period
 - Medications administered during this timeframe will be collected separately (i.e., each dose administered will be collected separately)
- Follow-up period (starts 120 hours following IP discontinuation)
 - Medications administered during this timeframe will be collected per the medication order

Vasopressors

- Administration of a continuous IV vasopressor infusion during IP administration or within 24 hours following IP discontinuation will be collected in the Prior and Concomitant Medication eCRF.

For some of the concomitant medications only the highest dose administered will be required in the eCRF. Reference the eCRF Completion Guidelines for guidance.

5.2.1 Permitted Treatment

To qualify for inclusion ([Section 4.1](#)), the participant must have received an acute treatment with any two or more of the following agents for treatment of the current episode of SE: benzodiazepines, IV fosphenytoin/phenytoin, IV valproic acid, IV levetiracetam, IV lacosamide, IV phenobarbital, IV brivaracetam, or IV phenobarbital. Taking any of these drugs alone or in combination is acceptable. Fosphenytoin/phenytoin will be counted as one (1) IV AED. Levetiracetam and brivaracetam will be counted as two (2) IV AEDs.

If the participant is receiving an oral AED to manage a chronic medical condition, (e.g., epilepsy, migraine, or neuropathic pain), the AED is acceptable and may continue unchanged. This maintenance treatment does not count towards the SE treatment failures required to qualify for this study.

The site will record the reason for each AED dose during IP administration in the appropriate CRF page.

5.2.2 Prohibited Treatment

If a participant progresses at any time during the study to an IV anesthetic (e.g., midazolam, propofol, thiopental, or pentobarbital) given with the primary intent specifically to treat seizures or achieve burst suppression IP administration will be discontinued without taper but the participant will continue in the study. Additional details can be found in [Section 4.5](#).

Concomitant use of IV products containing Captisol® during IP administration is prohibited (see exclusion criterion #7 and Appendix 4).

6 INVESTIGATIONAL PRODUCT

6.1 Identity of Investigational Product

The IP is ganaxolone IV solution, 1 mg/mL, or placebo which will be provided in 500 mL glass bottles with a grey stopper, purple flip-off cap and aluminum overseal. Each 500 mL bottle contains 425 mL of a sterile solution. The IP is provided as a unit dose bottle. Placebo will only be used for the double-blind phase of the study. Should the study transition to open-label, the ganaxolone IV solution administered as IP will be identical to the ganaxolone IV solution administered during the double-blind phase.

The active formulation consists of a sterile solution of ganaxolone drug substance that has been solubilized by complexation with Captisol® (Betadex Sulfoxetyl Ether Sodium). The drug product is terminally heat-sterilized.

On 01 June 2022 the Drug Enforcement Administration (DEA) issued its interim final rule placing ganaxolone, including its salts, in schedule V of the Controlled Substances Act. The DEA drug code for Ganaxolone (commercial name, Ztalm) is 2401.

For more details on the composition of the ganaxolone IV solution, 1 mg/mL refer to the Pharmacy Manual.

6.1.1 Blinding the Treatment Assignment

6.1.2 Double-Blind Phase

During the double-blind phase of the study, all participating staff involved in the evaluation and execution of the study will remain blinded to the participant's treatment assignment.

6.1.3 Open-Label Phase

If the study transitions to an open-label phase (refer to [Section 10.7](#)), blinding will not be applicable for new participants enrolled in the open-label phase of the study.

6.2 Administration of Investigational Product(s)

6.2.1 Interactive Response Technology for Investigational Product Management

Interactive Response Technology (IRT) will be utilized for the following tasks:

- IP allocation (double-blind phase only)
- Randomization (double-blind phase only)
- Supply management
- Inventory management and supply ordering
- Expiration date tracking
- Returns
- Emergency unblinding (double-blind phase only)

Details of the system and a system user manual will be provided for the investigator files at each site.

6.2.2 Allocation of Participants to Treatment

6.2.2.1 Double-Blind Phase

The actual treatment given to individual participants is determined by a randomization schedule. Participant identification numbers are assigned prior to dosing. Within each site (numbered uniquely within a protocol), participant numbers are assigned in the sequence of participant presentation for study participation. To allow for timely delivery of IP to the hospital unit, the IP bottles may be allocated for use in the IRT prior to the participant meeting all eligibility criteria to avoid impact to standard of care. Investigational product will not be administered until eligibility has been determined. Enrollment is defined as the initiation of IP infusion.

6.2.2.2 Open-Label Phase

All eligible participants enrolled under the open-label phase of the study will receive ganaxolone IV solution added to SE standard of care. No randomization will occur.

As per the double-blind phase, within each site, participant numbers will be assigned in the sequence of participant presentation for study participation. Investigational product will not be

administered until eligibility has been determined. Enrollment is defined as the initiation of IP infusion.

- A 30 mg bolus dose (over ~3 minutes) will be administered with a continuous infusion of 80 mg/hour for 2 hours followed by a continuous infusion rate of 40 mg/hour for 10 hours, and then 20 mg/hour for the remaining 12 hours of Day 1.
- On Day 2, from 24 to 36 hours following IP initiation, the continuous infusion rate of 20 mg/hour can be increased up to a maximum rate of 45 mg/hour until the start of the taper at 36 hours. The infusion rate will be determined by the investigator to best manage seizure relapse and cannot exceed the rate of 45 mg/hour between 24- and 36- hours following IP initiation.
- To taper IP, beginning 36 hours following IP initiation, the infusion rate will be reduced by 33.3% every 4 hours until the infusion is stopped or until the infusion rate becomes too low to sustain the IV line.
- Note: If, according to the investigator's clinical judgment, IP taper needs to start sooner than 36 hours after initiation, the infusion rate will be decreased by 33.3% of the rate at the beginning of the IP taper every 4 hours.
- At the time the IP infusion is discontinued, the participant will progress to the follow-up period assessments/procedures.

Table 4. Dosing for Participants ≥ 40 kg (on a mg/hour basis)

Days	Start Time from IP Initiation	IP Dose	IP Infusion Rate (mL/hour)	Duration
Day 1	0 hours: bolus dose via syringe or infusion pump	30 mg ^a	N/A	3 minutes (0.05 hours)
Day 1	0 hours through 2 hours following IP initiation: continuous infusion, started with bolus	80 mg/hr	80	2 hours
Day 1	2 hours through 12 hours following IP initiation	40 mg/hr	40	10 hours
Day 1	12 hours through 24 hours following IP initiation	20 mg/hr	20	12 hours
Day 2 ^b	24 hours through 36 hours following IP initiation	20 - 45 mg/hr	20 - 45	12 hours
Taper				
Day 2 ^c	36 through 48 hours following IP initiation (12-hour taper)	13 - 30 mg/hr	13 - 30	4 hours
		9 - 20 mg/hr	9 - 20	4 hours
		6 - 13 mg/hr	6 - 13	4 hours

IP = investigational product.

- a. The 30 mg bolus is administered over ~3 minutes.
- b. On Day 2 (24 through 36 hours), the continuous infusion rate can be increased from 20 mg/hour to a maximum rate of 45 mg/hour at any time, if needed, to manage seizure relapse or other medical reason.
- c. To taper the IP, the infusion rate at the 36-hour following IP initiation timepoint will be reduced by 33.3% every 4 hours until the infusion rate is stopped or if the infusion rate becomes too low to sustain the infusion line, at which point it will be stopped. The first taper will be 33.3% from the current infusion rate (e.g., if the current infusion rate is 20 mg/hr, the first taper will be 13 mg/hr) the second taper will be 33.3% from the first tapered infusion rate (e.g., if the current infusion rate is 20 mg/hr, the second taper will be 9 mg/hr), and the final taper will be 33.3% from the previous tapered infusion rate (e.g., if the current infusion rate is 20 mg/hr, the final taper will be 6 mg/hr). If, in the investigator's judgment, the taper needs to start at an earlier timepoint during the treatment period, the infusion rate at the start of the first taper will be decreased by 33.3% every 4 hours as described.

6.2.3.2 Participants weighing <40 kg will be dosed on a per kilogram basis:

- A 0.75 mg/kg bolus dose (over ~3 minutes) will be administered with a continuous infusion at a dose of 2.0 mg/kg/hour for 2 hours followed by a continuous infusion dose of 1.0 mg/kg/hour for 10 hours, and 0.5 mg/kg/hour for the remaining 12 hours of Day 1.
- On Day 2, 24 to 36 hours following IP initiation, the continuous infusion rate of 0.5 mg/kg/hour can be increased up to a maximum of 1.125 mg/kg/hour until the start of IP taper at 36 hours. The infusion rate will be determined by the investigator to best manage seizure relapse and cannot exceed the rate of 1.125 mg/kg/hour during hours 24 to 36 of Day 2 at any time.
- To taper IP, beginning 36 hours following IP initiation, the infusion rate will be reduced by 33.3% every 4 hours until the infusion is stopped or until the infusion rate becomes too low to sustain the IV line.

Note: If, according to the investigator's clinical judgment, IP taper needs to start sooner than 36 hours after initiation, the infusion rate will be decreased by 33.3% of the rate at the beginning of the IP taper every 4 hours.

- At the time the IP infusion is discontinued the participant will progress to the follow-up period assessments/procedures.

Table 5. Dosing for Participants <40 kg (on a mg/kg/hour basis)

Days	Start Time from IP Initiation	IP Dose	IP Infusion Rate (mL/kg/hour) ^a	Duration
Day 1	0 hours: bolus dose via syringe or infusion pump	0.75 mg/kg ^b	N/A	3 minutes
Day 1	0 hours through 2 hours following IP initiation continuous infusion, started with bolus	2.0 mg/kg/hr	2.0	2 hours
Day 1	2 hours through 12 hours following IP initiation	1.0 mg/kg/hr	1.0	10 hours
Day 1	12 hours through 24 hours following IP initiation	0.50 mg/kg/hr	0.50	12 hours
Day 2 ^c	24 hours through 36 hours following IP initiation	0.50 – 1.125 mg/kg/hr	0.50 - 1.125	12 hours
Taper				
Day 2 ^d	36 through 48 hours following IP initiation (12-hour taper)	0.34 – 0.75mg/kg/hr	0.34 - 0.75	4 hours
		0.22 – 0.51mg/kg/hr	0.22 - 0.51	4 hours
		0.15 – 0.34mg/kg/hr	0.15 - 0.34	4 hours

IP = investigational product.

- Reference the Pharmacy Manual for IP infusion rates based on mg/kg/hour dosing.
- The 0.75 mg/kg bolus is administered over ~ 3 minutes.
- On Day 2 (24 through 36 hours), the continuous infusion dose can be increased from 0.5 mg/kg/hour to a maximum dose of 1.125 mg/kg/hour at any time, if needed, to manage seizure relapse or other medical reason.
- To taper the IP, the infusion rate at the 36-hour following IP initiation timepoint will be reduced by 33.3% every 4 hours until the infusion rate becomes too low to sustain the infusion line, at which point it will be stopped. The first taper will be 33.3% from the current infusion rate (e.g., if the current infusion rate is 0.50 mg/kg/hr, the first taper will be 0.34 mg/kg/hr), the second taper will be 33.3% from the first tapered infusion rate (e.g., if the current infusion rate is 0.50 mg/kg/hr, the second taper will be 0.22 mg/kg/hr), and the final taper will be 33.3% from the previous tapered infusion rate (e.g., if the current infusion rate is 0.5 mg/kg/hr, the final taper will be 0.15 mg/kg/hr). If, in the investigator's judgment, the taper needs to start at an earlier timepoint during the treatment period, the infusion rate at the start of the first taper will be decreased by 33.3% every 4 hours as described.

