- To taper IP, beginning 36 hours following IP initiation, the infusion rate will be reduced by 33.3% every 4 hours until the infusion is stopped or until the infusion rate becomes too low to sustain the IV line.
Note: If, according to the investigator's clinical judgment, IP taper needs to start sooner than 36 hours after initiation, the infusion rate will be decreased by 33.3% of the rate at the beginning of the IP taper every 4 hours.
- At the time the IP infusion is discontinued, the participant will progress to the follow-up period assessments/procedures.

Participants weighing <40 kg will be dosed on a per-kilogram basis:

- A 0.75 mg/kg bolus dose (over ~3 minutes) will be administered with a continuous infusion at a dose of 2 mg/kg/hour for 2 hours followed by a continuous infusion dose of 1 mg/kg/hour for 10 hours, and 0.5 mg/kg/hour for the remaining 12 hours of Day 1 (time 0 to 24 hours).
- On Day 2, 24 to 36 hours following IP initiation, the continuous infusion rate of 0.5 mg/kg/hour can be increased up to a maximum of 1.125mg/kg/hour until the start of IP taper at 36 hours. The infusion rate will be determined by the investigator to best manage seizure relapse and cannot exceed a rate of 1.125 mg/kg/hour during hours 24 to 36 of Day 2.
- To taper IP, beginning 36 hours following IP initiation, the infusion rate will be reduced by 33.3% every 4 hours until the infusion is stopped or until the infusion rate becomes too low to sustain the IV line.
Note: If, according to the investigator's clinical judgment, IP taper needs to start sooner than 36 hours after initiation, the infusion rate will be decreased by 33.3% of the rate at the beginning of the IP taper every 4 hours.
- At the time the IP infusion is discontinued, the participant will progress to the follow-up period assessments/procedures.

Investigational product infusion precautions:

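### The protocol states two incompatible calculations for the same early taper: a fixed decrement in the dosing notes and a compounding reduction in the footnotes to Tables 4 and 5

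*Protocol*

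**What the plan says.** Three parts of the protocol bear on the taper.

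- **Scheduled-taper bullet** (synopsis, 6.2.3.1, 6.2.3.2): from hour 36, "the infusion rate will be reduced by 33.3% every 4 hours until the infusion is stopped" or the rate is too low to keep the line open. The bullet does not say what the percentage is taken of.
- **Early-taper note** directly below it, in the same three places: "the infusion rate will be decreased by 33.3% of the rate at the beginning of the IP taper every 4 hours". The base is fixed as the rate running when the taper begins.
- **Table 4 footnote c**: "the second taper will be 33.3% from the first tapered infusion rate", and then "the final taper will be 33.3% from the previous tapered infusion rate". It goes on to the early taper: "the infusion rate at the start of the first taper will be decreased by 33.3% every 4 hours as described". Table 5 footnote d says the same for participants under 40 kg.

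Tables 4 and 5 list three 4-hour taper steps over hours 36 to 48. SAP 3.1.6 reproduces both tables with their footnotes but not the early-taper note. SAP section 4 declares no changes from the protocol.

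**The concern.** The note and the footnotes address the same event, a taper that starts before hour 36, and give different arithmetic for it. A site that follows the note and a site that follows the footnotes would both be following the protocol, yet they would run different rates from the second step on and stop at different times.

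Dosing consistency is the first thing at stake. The stop time matters too. Discontinuation of the infusion starts the follow-up period (6.2.3, 7.1.3), sets the end of EEG recording (7.2.2.1) and times the discontinuation and 24-hour PK and laboratory samples (Tables 1 and 2). Two descriptive time-to-event summaries in the SAP (3.2.3.2, 3.2.3.3) may also be censored at completion of the infusion. Finally, someone who checks infusion records against the SAP's copy of the tables alone could mark a taper given under the note as non-compliant.

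**Working it through.** **Inputs.** Reduction of 33.3% every 4 hours (both rules). Three steps (Tables 4 and 5). Starting rates of 20 and 45 mg/h (Table 4, hours 24 to 36), 40 mg/h (Table 4, hours 2 to 12), and 0.50 and 1.125 mg/kg/h (Table 5).

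**Formulas**, with R the rate when the taper starts and k = 1, 2, 3:

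- Compounding (footnotes): R × (1 − 0.333)^k
- Fixed decrement (note): R × (1 − 0.333 × k)
- Taper dose: 4 h × the sum of the three rates

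**1. Reproducing the tables.** Compounding from 20 mg/h gives 13.34, 8.90 and 5.93; Table 4 has 13, 9 and 6. From 45 mg/h it gives 30.0, 20.0 and 13.4; Table 4 has 30, 20 and 13. From 0.50 mg/kg/h it gives 0.334, 0.222 and 0.148; Table 5 has 0.34, 0.22 and 0.15. From 1.125 mg/kg/h it gives 0.750, 0.500 and 0.334; Table 5 has 0.75, 0.51 and 0.34. Every difference in Table 5 is at most 0.01.

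**2. The fixed decrement against the same tables.** From 20 mg/h it gives 13.34, 6.68 and 0.02. From 45 mg/h it gives 30.0, 15.0 and 0.05. At step 2 that is 6.7 against 9 and 15 against 20; at step 3 it is about zero against 6 and 13. In Table 5, step 2 would be 0.167 and 0.376 mg/kg/h, where the table has "0.22 – 0.51mg/kg/hr". The tables follow compounding only.

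**3. An early taper under each rule.**

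| Start | Rule | 0–4 h | 4–8 h | 8–12 h | Taper dose |
|---|---|---|---|---|---|
| 20 mg/h | Footnotes | 13.34 | 8.90 | 5.93 | 113 mg |
| 20 mg/h | Note | 13.34 | 6.68 | 0.02 | 80 mg |
| 40 mg/h | Footnotes | 26.68 | 17.80 | 11.87 | 225 mg |
| 40 mg/h | Note | 26.68 | 13.36 | 0.04 | 160 mg |

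**4. At any starting rate.** Step 1 is the same. Step 2 is 0.334R under the note against 0.445R, and 0.334 / 0.445 = 0.75, so about 25% lower. The three steps sum to 1.002R against 0.667R + 0.445R + 0.297R = 1.409R. The ratio is 0.711, so the taper dose is about 29% lower. The infusion in effect ends at 8 h instead of 12 h, a difference of 4 h.

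**The case against.** The best reply is that the two texts can be harmonised. The footnote's sentence on early tapers resembles the note. Both could be taken only to name the starting rate (the one then running, not the hour-36 rate), with the footnote supplying the steps. The worked figures, the tables and the SAP all point to one algorithm. This reading does not survive the note's own words, which make the starting rate the base of every 4-hourly reduction. Nor can the note be treated as a deliberate separate rule for early tapers, because the footnotes cover that case and answer it differently.

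Several limits on the consequences do stand:

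- SAP 3.1.6 summarises total administered dose and infusion duration, and the PK analysis uses actual sampling times. Follow-up assessments move with the stop time by design.
- Protocol 8.1.7 says that lower doses given as part of discontinuation are not medication errors.
- Participants who progress to IV anesthesia for seizures stop without a taper (5.2.2), so neither rule applies to them.
- Receiving the product for under 2 hours is a listed scenario for stopping without a taper (6.2.6). An illustration from the 80 mg/h rate, which runs only in hours 0 to 2, would therefore be untypical.
- Randomization stopped at 100 (3.1.1), so rewording changes few or no future infusions.

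A reader might infer that the daily ceiling is at risk. The figures do not support that. A compounding taper begun from 40 mg/h at hour 12 gives 30 + 160 + 400 + 225 = 815 mg on Day 1, below the 833 mg limit, and the note's rule gives less.

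A reader might also infer that a co-primary result turns on the taper rule, since SAP 3.2.1.1 counts discontinuation of study treatment as non-response. The documents do not say whether an early taper counts as discontinuation or which time would be used, and they do not say how many early tapers occurred. That inference is unsupported.

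**Conclusion.** The inconsistency is real and lies in current text, in both weight groups: one situation, two infusion calculations. The difference is about 25% at the second step, about 29% of the taper dose and about 4 hours of infusion. It is a defect of wording with a bounded effect on analysis, because dose and duration are summarised as administered. No effect on an efficacy conclusion is shown.

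The sizes rest on three assumptions: the note is read literally; a compounding early taper runs the three 4-hour steps that the tables show (compounding alone never reaches zero); and the infusion is not stopped sooner because the rate is too low to sustain the line. The number of early tapers is not given. The Pharmacy Manual, to which Table 5 refers for rates, is not available here, so it is unknown whether sites received conflicting working instructions.

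**What to change.** Reconcile the early-taper note in the synopsis, 6.2.3.1 and 6.2.3.2 with Tables 4 and 5 and footnotes c and d, so that one calculation is stated for both weight groups. State the base of the percentage in the scheduled-taper bullet as well. Check the Pharmacy Manual and the SAP's copy of the tables against the result. Which calculation is retained is for the sponsor to decide.

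For the analysis, confirm that early tapers already given enter the SAP 3.1.6 summaries from recorded rates and stop times, and document which method each followed. Do not class a taper as a deviation solely because it followed one of the two stated rules.

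The cost is a wording change and a review of the infusion records for participants tapered early. No new data are needed.
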